#### 8.1 INITIAL CLINICAL DETAILS

The research nurse will collect the following information prior to randomisation:

- patient details (name, date of birth, hospital number)
- height and weight
- menopausal status
- oral contraceptive/ hormone replacement therapy usage
- name of hospital and breast surgeon
- date of diagnosis

- location of tumour at clinical examination
- dates of mammography and ultrasound
- use of pre-operative neo-adjuvant therapy.

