# **2.** AIMS AND OBJECTIVES

The overall aim of this randomised controlled trial is to determine the potential benefits to the patient and to the NHS of the addition of MR imaging to the routine techniques employed for loco-regional staging of primary breast cancer.

The primary objective of the study will be to evaluate the role of MR imaging with respect to:

i) Comparison of the repeat operation or mastectomy rates following primary excision between those planned by conventional triple assessment (clinical examination, X-ray mammography and fine needle aspiration cytology/ core biopsy) and those planned by a combination of triple assessment and dynamic contrast-enhanced MR imaging (DCE-MRI). This will include an economic evaluation from a societal perspective of the cost-effectiveness between the two arms.

The secondary objectives of the study will include:

- i) Determination of the ipsilateral breast tumour recurrence rate for both groups up to five years post-diagnosis.
- ii) Comparison of subsequent chemotherapy/ radiotherapy interventions between women planned by triple assessment and those planned by triple assessment and MR imaging combined.
- iii) An assessment of the quality of life and patient satisfaction with management decisions based on either triple assessment or triple assessment combined with MR imaging.
- iv) An investigation of the risk factors for referral for MR imaging. This will be determined by modelling the different and/or combined approaches to the loco-regional staging of primary breast cancer. This will involve multiple regression analysis of baseline information, including demographic data, history of exogenous hormone consumption and concurrent breast disease, data derived from X-ray mammography, ultrasound and MR imaging, and the cytology and histopathology findings.
- v) Evaluation and comparison of the accuracy of loco-regional staging by X-ray mammography, ultrasound and MR imaging, with reference to the tumour extent determined by histopathology of the resected specimens, in particular with respect to more extensive surgery.
- vi) Observation of the percentage of patients in whom a change in clinical management occurs after MR imaging.

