# 4. ELIGIBILITY

#### 4.1 INCLUSION CRITERIA

Patients must:

- be aged 18 years or over
- have undergone X-ray mammography (standard medio-lateral oblique, cranio-caudal and where appropriate paddle/ axillary views carried out within the guidelines of the NHS BSP), and ultrasound scanning (using a 7.5 to 13 MHz linear array transducer) during the current treatment episode
- have pathologically documented primary breast carcinoma, either from fine needle aspiration cytology or core biopsy
- be scheduled for wide local excision on the basis of existing results
- provide written informed consent.

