# 8. DATA COLLECTION

Data generated by all centres will be collected, monitored and computerised by the NYCTRU. All centres will be asked to complete a log of all patients who are approached to enter the trial including those who refuse randomisation. Data collection for randomised patients will include: initial clinical details pre-randomisation, surgical procedure performed, histopathology, postoperative information, hospital re-admission, and recurrence details as listed below. As some variations in ancillary management (e.g. radiotherapy) and pathological examination exist between centres, the current management policies of each centre will be recorded at baseline and adherence to these policies monitored.

Attempts have been made to reduce data collection to a minimum, with the majority of data being completed by the research nurse and much of the remainder being collected routinely within the framework of the NHS BSP.

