#### 11.2.4 RISK FACTORS FOR REFERRAL FOR MR IMAGING

Risk factors for referral for MRI will be determined by modelling for those patients where mammography and pathology findings do not agree (in terms of tumour presence and extent) whether or not the MRI does agree with the pathology (in terms of tumour presence and extent). This will involve multiple regression analysis of baseline information, including demographic data, history of exogenous hormone consumption and concurrent breast disease, data derived from X-ray mammography, ultrasound and MR imaging, and the cytology and histopathology findings.

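### The MR-referral model names concurrent breast disease and cytology as predictors, but no data-collection list records either, and it admits predictors that are unknown when referral is decided

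*Combined protocol and SAP*

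**What the plan says.** Secondary objective iv (section 2) is an investigation of the risk factors for referral for MR imaging, by multiple regression. Besides demographic data it names these inputs: "history of exogenous hormone consumption and concurrent breast disease, data derived from X-ray mammography, ultrasound and MR imaging, and the cytology and histopathology findings".

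Section 11.2.4 repeats the list. It begins "This will involve multiple regression analysis of baseline information, including demographic data, history of exogenous hormone consumption and concurrent breast disease" and closes with "ultrasound and MR imaging, and the cytology and histopathology findings". Cytology is named separately from histopathology in both places. The same section defines the model as "modelling for those patients where mammography and pathology findings do not agree (in terms of tumour presence and extent"), with the outcome being whether MRI does agree with pathology.

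On data, section 8 says that collection for randomised patients will include "initial clinical details pre-randomisation, surgical procedure performed, histopathology, postoperative information, hospital re-admission, and recurrence details as listed below". Section 8.1 then gives the baseline items under the words "The research nurse will collect the following information prior to randomisation".

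Section 4.1 requires every woman to "have pathologically documented primary breast carcinoma, either from fine needle aspiration cytology or core biopsy", so a diagnostic sample exists for everyone before randomisation.

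**The concern.** A model can be fitted with its stated predictors only if each one is recorded. Two of those named here have no field in any list, although the baseline form goes down to height, weight and dates of imaging.

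Timing raises a second difficulty. The objective is to learn who should be sent for MR, and such a rule can use only what is known before MR. Pre-operative pathology meets that condition and exists for every woman, but its result is not listed. Specimen pathology is listed, but it becomes available only after MR and surgery. If it stands in for the missing pre-operative result, the fitted model cannot be applied at the moment it is meant to serve.

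**Working it through.** The point is a comparison of lists, so the only arithmetic concerns the denominator.

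**1. Trial size.** Inputs from section 10.1: rates of 15% and 10%, 90% power, 5% two-sided, chi-squared without continuity correction. The formula per arm is n = [1.960·√(2·p̄·q̄) + 1.282·√(p₁q₁ + p₂q₂)]² / (p₁ − p₂)², with p̄ = 0.125.
- 2·p̄·q̄ = 2 × 0.125 × 0.875 = 0.21875
- p₁q₁ + p₂q₂ = 0.1275 + 0.09 = 0.2175
- n = 918 per arm after rounding up, 1836 in total, against the stated 1840

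The plan's figure is reproduced. The concern does not depend on it, except as the starting point for step 4.

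**2. Named predictors against listed sources.**

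| Predictor group (objective iv, 11.2.4) | Listed source |
|---|---|
| Demographic data | 6.2 and 8.1 |
| Exogenous hormones | 8.1 (contraceptive and HRT use) |
| Concurrent breast disease | no dedicated field |
| X-ray mammography, ultrasound | 8.2 |
| MR imaging | 8.3 |
| Cytology | none |
| Histopathology | 8.6 |

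Places searched for the two gaps:
- 6.2 holds identity, surgeon, confirmation of imaging, breast density, and confirmation of eligibility and consent.
- 8.1 has nine items. It includes the date of diagnosis but not the diagnostic result, and it has no breast-disease item.
- 8.2 holds imaging features and an imaging score.
- 8.3 records when and what kind of additional biopsy was done, without its result.
- 8.4, 8.5, 8.7 and 8.8 cover the management change, surgery, the post-operative period and follow-up. Neither item appears.
- 8.6 is framed around excised specimens. It collects the histopathology report, the cancer registry form, and lesion size, malignancy and distances.

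**3. Named predictors against the time of referral.**

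| Information | Known before MR? | Listed in section 8? |
|---|---|---|
| Demographics, hormone use, mammography, ultrasound | yes | yes |
| Diagnostic FNAC or core-biopsy result | yes | no |
| Concurrent breast disease, as known clinically | yes | no |
| MR findings | no | yes |
| Specimen histopathology | no | yes |

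Specimen histopathology has a further defect as a predictor. In 11.2.4 it defines who enters the model (mammography disagrees with pathology) and also defines the outcome (MRI agrees with pathology). MR findings form the other half of that outcome.

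**4. Who is affected.** The outcome requires an MRI, so only the MR arm contributes. With 1:1 allocation that is 1840 / 2 = 920 women at most. The restriction to discordant mammography and pathology reduces this further. The documents give no discordance rate for this population, so the final number cannot be stated.

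**The case against.** The strongest reply is that the lists are an outline and the forms themselves are not in the documents. Section 8 says that collection will include certain items, and its summary sentence omits even the imaging findings that 8.2 and 8.3 then list. It adds that part of the data comes routinely through the screening programme, and 8.6 collects the cancer registry form. Either route might carry the pre-operative result. This stands to the extent that absence from the database is not proved. It does not remove the point. The contents of those routes are not described, and the trial enrols women aged 18 or over without requiring screen detection, so programme data cannot be assumed to cover everyone.

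Four stronger readings are tempting, and the documents do not support them:
- A reader might infer that objective iv cannot be analysed. The outcome and most predictors have listed sources, so a reduced model can be fitted.
- A reader might infer that post-surgical tumour type is all that is held. The documents support only that the excised specimen is the sole listed source of pathology.
- A reader might apply the gap to all 1840 women. The items are unlisted for all of them, but the model uses only the discordant part of the MR arm.
- A reader might infer that the primary analysis is compromised by a post-randomisation covariate. Sections 11.1.1(ii) and 11.4 do not name specimen pathology. Covariates are to be decided before analysis, and 11.4 gives primacy to the unadjusted result. The risk is hypothetical.

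Two further replies stand in part. Eligibility makes a bare malignant result nearly constant, so what is lost is category, in situ or invasive status, type and grade. Section 8.2 describes all mass lesions, which is an indirect source on concurrent disease, though an imaging description is not a clinical record of it.

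**Conclusion.** The concern holds in a limited form. Two predictors named in objective iv and 11.2.4 have no field in any data-collection list, so on the lists as written the referral model cannot be fitted with its stated predictors. Separately, the specification admits specimen histopathology and MR findings, neither of which is available when referral is decided. That second fault would remain even if the missing items turned up in a routine source.

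The loss in the model's discrimination cannot be computed from the documents. The conclusion rests on two readings: that the section 8 lists reflect the forms, and that the model is meant to guide referral before MR, as its title indicates. The objective is secondary, and section 11 restricts formal testing to the primary endpoints. This is therefore a low-priority improvement, and the unadjusted primary analysis is not affected.

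**What to change.** - **8.1:** add the diagnostic FNAC or core-biopsy result (C or B category, in situ or invasive, type and grade where reported) and concurrent breast disease. Alternatively, name the routine source that supplies them for all women.
- **11.2.4:** restrict the predictors to values known before MR. Use pre-operative pathology in place of specimen histology and leave out MR findings. Both remain in use for defining the outcome.
- **11.4:** restrict candidate covariates to pre-randomisation values, which closes off the hypothetical problem in the adjusted analyses.
- **Section 2, objective iv:** align the predictor list with the revised 11.2.4.

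The cost is two extra items on a form the research nurse already completes. For women already randomised they are probably retrievable from the notes, which is an assumption. Type and grade will be incomplete where only FNAC was done, so the analysis needs a stated way of handling those gaps.

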#### 8.2 MAMMOGRAPHIC AND ULTRASOUND FINDINGS

The reporting radiologist will record the following information:

- name of radiologist
- background breast pattern on mammography
- location, size and morphological characteristics of all mass lesions, including margin delineation, density, halo and presence of microcalcifications
- presence of stromal deformity, skin changes and pathological nodes
- proximity of tumour to clinically relevant structures
- echo-pattern and presence of acoustic shadowing
- lesion(s) score based on NHS BSP criteria.

#### 8.3 MR IMAGING FINDINGS

The reporting radiologist will record the following data:

- name of radiologist
- location/ maximum diameter of index lesion
- presence, location and maximum diameter of additional multi-focal and or multi-centric lesions
- proximity of the multi-focal/ multi-centric lesions to the index tumour, skin, chest wall and nipple retro-areolar complex
- outcome of MR imaging, i.e. score for each lesion detected
- date/type of additional biopsy or intervention performed.

#### 8.4 CHANGE IN SURGICAL MANAGEMENT

Following MR imaging, the surgical management will be reviewed by the multidisciplinary team. A change to the proposed surgical management will be recorded by the named consultant breast surgeon as either:

- no action
- extended wide local excision
- conversion to mastectomy/quandrantectomy
- conversion to primary chemotherapy.

#### 8.5 SURGERY

The following information will be collected by the surgeon:

- dates of admission/surgery
- type of operation
- intra-operative complications and their management, including fluid replacement, analgesia, antibiotics, need for blood transfusion etc.

- length of time in theatre/anaesthetic time
- other health economics data.

#### 8.6 HISTOPATHOLOGY

Following weighing, serial sectioning of appropriately marked excised specimens (wide local excision or mastectomy) will be carried out with reference to the MR hard copy and in accordance with the guidelines in the NHS BSP publication 'Pathology reporting in breast cancer screening'. These core guidelines contain the 'Minimal dataset for breast cancer histopathology reports' published by the Royal College of Pathologists. A copy of the Histopathology report and the cancer registry form will be collected. The following additional information will be collected by the pathologist:

- size and malignancy of index and additional (multi-focal and / or multi-centric) lesions
- proximity of lesion(s) to skin, chest wall and nipple retro-areolar complex as appropriate
- distance between index and other lesions.
- number of blocks taken

#### 8.7 **POST-OPERATIVE INFORMATION**

The following information will be recorded by the research nurse for the period from operation to discharge:

- date of discharge
- post-operative complications and their management, including fluid replacement, analgesia, antibiotics, need for blood transfusion etc.
- follow-up arrangements.

#### 8.8 FOLLOW-UP

The following information will be recorded:

At 6 months:

- re-admissions to hospital including reasons and dates
- date and type of further surgery

#### At 12 months:

- usage of chemotherapy, radiotherapy, adjuvant therapy and entry into other trials
- tumour recurrences (date, site and method of diagnosis)

#### Up to 5 years:

- tumour recurrences (date, site and method of diagnosis)
- status (date and cause of death if applicable).

# 9. ENDPOINTS

#### 9.1 **PRIMARY ENDPOINTS**

#### 9.1.1 REPEAT OPERATION OR MASTECTOMY RATE

The repeat operation or mastectomy (following primary excision) rates will be compared between the two principles under investigation.

#### 9.1.2 ECONOMIC EVALUATION

The economic evaluation from a societal perspective of the two principles under investigation, will include within-trial cost-effectiveness relating differential costs to ipsilateral breast tumour recurrence rate out to 60 months; and an extrapolated cost-effectiveness analysis, where longer term costs and quality-adjusted survival will be modelled on the basis of any difference in trial estimates of recurrence.

#### 9.2 SECONDARY ENDPOINTS

#### 9.2.1 RECURRENCE RATE

Five-year local recurrence rates will be compared.

#### 9.2.2 CHEMOTHERAPY/RADIOTHERAPY INTERVENTIONS

Subsequent chemotherapy/radiotherapy interventions will be compared between women, planned by triple assessment or by triple assessment and MR imaging combined.

#### 9.2.3 QUALITY OF LIFE AND PATIENT SATISFACTION

Quality of life as assessed by the FACT-B, and anxiety and depression as assessed by the HADS, at 8 weeks post randomisation and 6 and 12 months post surgery. Concerns about tumour recurrence post-operatively will be assessed by an ad-hoc questionnaire at 8 weeks post randomisation and 6 and 12 months following surgery.

#### 9.2.4 **RISK FACTORS FOR REFERRAL FOR MR IMAGING**

The risk factors for referral for MR imaging will be determined by modelling the different and/or combined approaches to the loco-regional staging of primary breast cancer.

#### 9.2.5 EFFECTIVENESS OF IMAGING

Correlation of histopathology results with imaging findings will be performed with particular reference to:

- detection and classification of lesions
- maximum diameter of all foci of invasive/in situ carcinoma present

- anatomical relationship of multi-centric/multi-focal disease to the index lesion and other structures
- location and extent of additional pathologies.

In addition the inappropriate more extensive surgery\* rates for combined triple assessment and MR imaging will be examined.

\* Inappropriate more extensive surgery is defined as: pre-operative conversion from wide local excision to more extensive surgery (eg quadrantectomy, mastectomy etc) based on triple assessment plus MR imaging, however subsequent histopathological examination of the resected specimen reveals less extensive breast cancer, which could reasonably have been treated by wide local excision alone.

#### 9.2.6 CHANGE IN CLINICAL MANAGEMENT

Patients in whom a change in clinical management occurred after MR imaging will be observed.

#### 9.2.7 CLINICAL SIGNIFICANCE OF < 5 MM MR-ONLY DETECTED LESIONS

The clinical significance of < 5 mm diameter lesions not amenable to further pre-operative diagnosis will be ascertained from repeated MR imaging at 12 months post -radiotherapy, and the management changes prompted by their detection documented.

### **10. STATISTICAL CONSIDERATIONS**

#### **10.1** SAMPLE SIZE

Assuming that the addition of MR imaging will reduce overall repeat operation or mastectomy rates following inadequate wide local excision from approximately 15% to 10%, a total of 1840 patients is required, using a chi-squared test without continuity correction, to detect benefit with 90% power at the 5% (2-sided) significance level (Machin et al, 1997).

#### **10.2** ACCRUAL

Accrual at centres will be restricted by scanner, research nurse and radiologist availability. It is anticipated that consent rate of 50% of patient approached will be achievable. We therefore propose to recruit up to 50 centres over the course of the trial that will each recruit approximately 1 patient per week. Randomisation will be equally split to MR imaging or no MR imaging. As the project is funded by the NHS HTA programme, we anticipate that NCRN research will assist in the recruitment process.

# **11.** ANALYSIS PLAN (OUTLINE)

Analysis of the study will be performed in two stages, firstly at completion of the initial follow-up following surgery, and secondly, once the five-year follow-up has been completed in all patients. The primary analysis will be on an intention-to-treat basis. All hypothesis tests will be 2-sided and

at the 5% level: p-values less than 0.05 will be considered to be statistically significant. Formal hypothesis testing will be restricted to the primary endpoints only.

Inference will be based on available data only. Sensitivity analysis will be carried out if there are missing data to test the robustness of the conclusions, the results of which will be fully reported.

#### **11.1 PRIMARY ENDPOINTS**

#### 11.1.1 REPEAT OPERATION OR MASTECTOMY RATE

- i) The chi-squared test without continuity correction will be used to compare the proportion of patients in the two trial arms who have a repeat operation or mastectomy. 95% confidence intervals will be reported.
- ii) A logistic regression model will be fitted, adjusting for the stratification variables and other covariates that are identified as being prognostic of outcome. The adjusted analysis will be reported with the unadjusted analysis.
- iii) The impact on the primary endpoint of those patients who choose mastectomy, rather than WLE outside of the definitions for mastectomy within the trial, will be investigated in a sensitivity analysis. In this analysis we will assume that such patients would either all have undergone repeat operation or mastectomy (following initial surgery) or had no further surgery, and investigate how this affects the conclusions in the primary analysis.
- iv) Multi-level modelling will be performed to explore whether there is a surgeon effect, and within the MRI arm whether there is a radiologist effect.

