#### **13.3 DATA MONITORING**

Data will be monitored for quality and completeness by the central trials office. At least one attempt will be made to recover data from incomplete forms; reminders will be sent to patients if postal questionnaires are not returned on time. The CTRU will intermittently conduct source data verification exercises on a sample of patients. In addition, the following issues will be monitored: the use of adjuvant treatment and the standard management policy at the various hospitals, the time

from consultation to MR scan and from consultation to surgery, and mastectomy rates due to patient request.

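### The sensitivity analysis for patient-choice mastectomy has no scenario that differs by arm, so with similar numbers in each arm it can make a fragile result look robust

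*Combined protocol and SAP*

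**What the plan says.** Section 11.1.1 item iii) plans a sensitivity analysis for women who choose mastectomy instead of wide local excision for reasons outside the trial's definitions. There are two scenarios. In the first, "such patients would either all have undergone repeat operation or mastectomy" after initial surgery; in the second, none had further surgery. The stated aim is to see whether the conclusion of the primary analysis changes.

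The rule speaks of these women as a single group. It does not mention the arms, and no other section supplies a scenario that treats the arms differently. Section 11 promises sensitivity analysis for missing data but names no scenarios.

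Section 13.3 lists "mastectomy rates due to patient request" among the items to be monitored. It gives no expected number and no split by arm.

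The primary comparison is set out in section 11.1.1 item i): "The chi-squared test without continuity correction will be used to compare the proportion of patients in the two trial arms". Section 11 adds: "The primary analysis will be on an intention-to-treat basis".

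**The concern.** For a woman who goes straight to mastectomy by choice, the outcome after wide local excision is unknown. A sensitivity analysis for such women should show how far the treatment difference could move under the possible values of that outcome. Setting all of them to the same value moves both arms in the same direction. If the numbers per arm are similar, the shifts cancel and the difference hardly changes, whatever the truth is.

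What is at stake is the robustness statement that will accompany the primary result. Two scenarios that agree with the main analysis would be read as evidence that choice mastectomies do not matter. With similar numbers in each arm, that agreement is largely built in. A null result has the same problem, because two scenarios that both show no difference would look equally reassuring.

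**Working it through.** **Inputs from the protocol.** Section 10.1 assumes a reduction "from approximately 15% to 10" per cent, states that "a total of 1840 patients is required", and sets the design "to detect benefit with 90% power at the 5% (2-sided) significance level", "using a chi-squared test without continuity correction". Allocation is 1:1 (section 6.2), so there are 920 women per arm.

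**The plan's own figure.** With the pooled-variance formula and no continuity correction,

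n per arm = [1.96·√(2·0.125·0.875) + 1.2816·√(0.15·0.85 + 0.10·0.90)]² / 0.05² = 917.3, rounded up to 918.

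That is 1836 in total, in line with 1840. Power at 920 per arm is 90.1%. The sample size is sound and is not at issue.

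**Assumptions.** The documents give no chooser rate, so I take 1% to 5% per arm (9, 18, 28 or 46 of 920). Choosers stay in the denominators, in line with intention to treat. The base case is 138 v 92 events (15% v 10%, control v MRI) among the other women.

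**Algebra.** Let kC and kM be the numbers of choosers in the control and MRI arms, and D the risk difference (control minus MRI) when all choosers count as non-events.

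- Planned, none: D
- Planned, all: D + (kC − kM)/920
- Bound 1 (control none, MRI all): D − kM/920
- Bound 2 (control all, MRI none): D + kC/920

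The planned pair spans |kC − kM|/920. The bounds span (kC + kM)/920. With 18 choosers in each arm the planned span is 0, and the full span is 36/920 = 3.9 points. With choosers in one arm only, the two spans are equal.

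**Equal numbers per arm, 138 v 92** (uncorrected chi-squared, z = difference / √(2·p̄(1−p̄)/920), where p̄ is the pooled proportion):

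| Choosers per arm | Planned, none | Planned, all | Bound 1 (control none, MRI all) |
|---|---|---|---|
| 9 (1%) | 5.0 points, p=0.0012 | 147 v 101: 5.0 points, p=0.0017 | 138 v 101: 4.0 points, p=0.010 |
| 18 (2%) | 5.0 points, p=0.0012 | 156 v 110: 5.0 points, p=0.0023 | 138 v 110: 3.0 points (95% CI −0.1 to 6.2), p=0.056 |
| 28 (3%) | 5.0 points, p=0.0012 | 166 v 120: 5.0 points, p=0.0031 | 138 v 120: 2.0 points, p=0.23 |
| 46 (5%) | 5.0 points, p=0.0012 | 184 v 138: 5.0 points, p=0.0048 | 138 v 138: 0.0 points, p=1.0 |

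Worked example for 138 v 110: p̄ = 248/1840 = 0.1348; standard error = √(2·0.1348·0.8652/920) = 0.01592; z = (28/920)/0.01592 = 1.91; p = 0.056.

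**When the planned pair first misses the change.** The smallest equal number per arm at which both planned scenarios stay below 0.05 and bound 1 does not is 18 (2.0%) at 138 v 92, 10 (1.1%) at 138 v 100, and 4 (0.4%) at 138 v 106.

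**Null result.** At 138 v 138 both planned scenarios give a difference of 0. The bounds become significant from 32 choosers per arm (3.5%).

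**Unequal numbers, 138 v 92:**

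| Choosers, control / MRI | Planned, all | Bound 1 |
|---|---|---|
| 0 / 28 | 2.0 points, p=0.23 | 2.0 points, p=0.23 |
| 9 / 28 | 2.9 points, p=0.074 | 2.0 points, p=0.23 |
| 18 / 28 | 3.9 points, p=0.019 | 2.0 points, p=0.23 |

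The weakness disappears when choosers fall in one arm. It remains under moderate imbalance.

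**The case against.** **Mechanism.** The trial is open, so a reader might infer that women in the MRI arm will ask for mastectomy because MR showed more disease, and that assumptions differing by arm are therefore the plausible ones. The documents do not support that step. Section 5.2.1 already places mastectomy after MR-detected extension, or after biopsy-positive multi-centric disease, within the trial pathway. Item iii) covers only mastectomy outside those definitions, so most MR-driven conversions are not the women in question. Some residual group is possible, such as women worried by small or biopsy-negative lesions, but the documents say nothing about its size.

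**Imbalance.** If MR did prompt extra requests, choosers would be more numerous in the MRI arm, and the planned 'all' scenario would then move the result. At 138 v 103 events with 2 control and 9 MRI choosers it gives 140 v 112, p=0.058, so the plan itself would flag fragility. This stands, and it limits the point to similar or moderately unequal numbers.

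**Extremity.** Bound 1 needs every MRI chooser and no control chooser to have required further surgery. A large but less extreme contrast, 50% v 10% among 18 choosers per arm at 138 v 92, gives 139.8 v 101 expected events and p=0.007. This also stands: the opposite-direction scenarios are limits, not likely truths.

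**Weight.** Section 11 is headed as an outline, this is one sensitivity analysis, and request mastectomies are monitored, so the numbers can be inspected. That lowers the priority. It does not supply the missing scenarios, because the split by arm is unknown in advance.

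**Conclusion.** The point holds in limited form. Item iii) has no scenario that differs by arm. With similar numbers of choosers in the two arms, its two scenarios cannot move the risk difference appreciably, so their agreement with the main analysis says little about robustness.

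At the full design effect the conclusion could change unnoticed from about 2% choosers per arm (18 of 920), and from fewer if the observed effect is smaller. At 1% with the full design effect the planned analysis and the bound agree. These sizes rest on assumed chooser numbers and on keeping choosers in the denominators.

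It would go too far to say that the planned analysis will mislead, or that the opposite extremes are the realistic cases. The primary test and the sample size are unaffected. Priority: minor.

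**What to change.** Extend section 11.1.1 item iii) with text such as:

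*The number of patients choosing mastectomy outside the trial's definitions will be reported by arm. In addition to the two common scenarios, two opposite-direction scenarios will be run as bounds: control none with MRI all, and control all with MRI none. Preferably these will be the corners of a grid that varies the assumed share needing further surgery among such patients separately in each arm. The report will state where on the grid the primary conclusion changes.*

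The grid is the better form, because it lets the reader judge whether the tipping point is credible and does not rest the argument on the extremes.

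The cost is one short paragraph and a few extra runs on data already held. It needs no new data, no change to sample size or primary test, and no change to patient care.
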